#### **14.1.1 Subgroup analyses**

In order to examine the consistency of the treatment effect, the MMRM model used for the primary analysis will also be used within the following subgroups, using the ITT population:

- ULT usage (yes/no).
- BMI ( $<30.0$  and  $\geq 30.0$  kg/m^2).
- Age ( $<65$  years and  $\geq 65$  years).
- Sex (male, female).
- Race (White and Other).
- Renal function (eGFR category  $\geq 90$ ,  $\geq 60 - <90$ ,  $\geq 30 - <60$ ).
- Usage of rescue medication up to 72 hours during for the first flare (yes/no).

For each subgroup, the estimated change in pain intensity in each treatment group (anakinra and triamcinolone), the estimated difference in change in pain intensity between treatments and the corresponding 95 % confidence intervals will be obtained from the model. P-values will not be presented. Further, the change in pain intensity will also be evaluated for the 2 anakinra doses for each subgroup.

The estimated difference in change in pain intensity between anakinra and triamcinolone and the corresponding 95 % confidence intervals will also be presented graphically in a forest plot.

To avoid too small subgroups in the analysis regarding race, American Indian or Alaska Native, Asian, Black or African American, Native Hawaiian or Other Pacific Islander will be grouped together with Other.

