1. 52 weeks after randomization of the last patient in the study

or

2. 104 weeks after randomization of the individual patient

whichever occurs first.

If the IMP treatment started week 40 or later in case 1), or week 92 weeks in case 2), the Week 12 visit will replace the End-of-study follow-up by phone.

All patients will have their follow-up visits/phone calls, irrespective of treatment withdrawal or use of rescue medication.

Subsequent flares occurring before the Day 15 visit of the latest flare (Visit 4) will be treated with permitted rescue medication i.e., no IMP will be administered.

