7.5.5.4 Use of rescue medication

Patients who have difficulty in tolerating their pain are allowed to take rescue medication as needed after the 24-hour post-dose pain assessment but not within 6 hours before the 48- and 72-hour post-dose pain assessments.

Rescue medication can be used at the discretion of the investigator and should be prescribed according to the product label; contraindications, interactions and precautions.

Permitted rescue medication includes paracetamol/acetaminophen (up to 1000 mg 4 times daily) and/or codeine (up to 50 mg 4 times daily) or short acting tramadol (up to 100 mg 4 times daily).

Topical ice/cold packs may also be used as rescue therapy.

However, patients will be permitted to continue thrombosis prophylaxis with low dose acetyl salicylic acid (≤ 325 mg/day).

At the discretion of the investigator, patients still having insufficient relief with above drugs after the 72-hour post-dose pain assessment are allowed to take oral prednisone, prednisolone or equivalent at a dose up to 0.5 mg/kg per day for a maximum of 5 days.

Subsequent flares occurring before Day 15 of the latest flare will be treated with permitted rescue medication.

The name, dose, date and time of all rescue medication taken at site will be recorded in the eCRF at Visit 1 to 4 of each flare. Rescue medication taken at home between Visit 1 and 4 of each flare will be recorded in the patient diary.

7.5.5.5 Clinical signs of the most affected joint (index joint tenderness, swelling and erythema)

The investigator will assess the tenderness (on the basis of palpation or passive motion) of the index joint on a 4-point Likert scale (0=no pain, 1=mild/patient states there is pain when touched, 2=moderate/patient states there is pain and winces, 3=severe/patient states there is pain, winces and withdraws).

The investigator will assess the swelling of the index joint on a 4-point Likert scale (0=no swelling, 1=mild swelling, 2=moderate swelling, 3=severe swelling or bulging beyond joint margins).

The investigator will assess erythema of the index joint as either “present” or “absent”.

For each flare, assessments of joint tenderness, swelling and erythema will be performed and recorded in the eCRF at baseline, 72 hours, Day 8 and Day 15.

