9.3.9 Exploratory subgroup analyses

In order to examine the consistency of the treatment effect, the primary analysis will be repeated within predefined subgroups using the ITT population. These subgroups will include the randomization strata, ULT usage (yes/no) and BMI (<30.0 and \geq 30.0 kg/m²), as well as age (<65 years and \geq 65 years), sex, race, renal function (CKD stage 1, 2 and 3) and usage of rescue medication during the first flare (yes/no). For each subgroup, the estimated change in pain intensity in each treatment group (anakinra and triamcinolone), the estimated difference in change in pain intensity between treatments and the corresponding 95% confidence intervals will be presented. P-values will not be presented. Further, the change in pain intensity will also be evaluated for the two anakinra doses for each subgroup.

Further subgroup analyses may be defined in the statistical analysis plan.

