### 3.3.2 Secondary efficacy endpoints

The following secondary endpoints will be assessed for the first flare and subsequent flares. All comparisons versus baseline (pre-dose measurement at Visit 1) will be made against the baseline of the first and subsequent flares, respectively.

- Time to onset of effect (defined as  $\geq 20$  % change from baseline pain intensity on VAS).
- Time to response (defined as  $\geq 50$  % change from baseline pain intensity on VAS).
- Response (defined as  $\geq 50$  % change from baseline pain intensity on VAS) at 24, 48 and 72 hours, Day 8 and Day 15 (yes/no).
- Resolution of pain (defined as  $< 10$  mm on VAS) at 72 hours, Day 8 and Day 15 (Yes/No).
- Time to resolution of pain (defined as  $< 10$  mm on VAS).
- Time to intake of rescue medication from first IMP administration.
- Type and number of occasions of intake of rescue medication taken from first IMP administration to Day 8.
- Patient's assessment of global response to treatment (5-point Likert scale) at 72 hours, Day 8 and Day 15.
- Physician's assessment of global response to treatment (5-point Likert scale) at 72 hours, Day 8 and Day 15.
- Physician's assessment of clinical signs at 72 hours, Day 8 and Day 15 in index joint tenderness, swelling and erythema.
- Change from baseline in the inflammatory biomarkers CRP and SAA at 72 hours, Day 8 and Day 15.

Additional assessment for the subsequent flares:

- Change in patient-assessed pain intensity in the index joint as measured by VAS score from baseline to 24 to 72 hours (average of the assessments performed at 24, 48 and 72 hours).
- Change from baseline in patient-assessed pain intensity in the index joint as measured by VAS score at 6, 12, 18, 24, 36, 48, 72 hours and Days 5, 6, 7 and 8.
- Change from baseline in patient-assessed pain intensity in the index joint as measured by a 5-point Likert scale at 6, 12, 18, 24, 36, 48, 72 hours and Days 5, 6, 7 and 8.

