#### **14.3.1.5 Rescue medication**

Time to first intake of rescue medication during the first flare will be analyzed using a stratified log-rank test, with ULT use (yes, no) and BMI ( $<30.0$ ,  $\geq 30.0$  kg/m^2) as stratification factors (see Section 18.22). Based on this model, the estimated hazard ratio (anakinra vs. triamcinolone), 95 % confidence interval and p-value will be presented. Further, the hazard ratios for the comparisons of the 2 different anakinra dose groups versus triamcinolone will also be estimated, with corresponding 95 % confidence intervals and p-values.

The hazard ratio and its confidence interval will be estimated based on Peto's method (see Section 14.3.1.2). Patients with only baseline values and patients with no values will be censored at baseline, i.e. will not be included in the analysis.

Time to first intake of rescue medication will also be presented graphically for the two dose groups of anakinra and triamcinolone.

In addition, the proportion and number of patients who took rescue medication from the first IMP administration up to 12 hours, >12 to 24 hours, >24 to 48 hours, >48 to 72 hours, >72 hours to Day 8, and >Day 8 to Day 15 in the different treatment groups will be presented. The proportion and number of patients with 0, 1, 2, 3 or more than 3 occasions with rescue medications as well as descriptive statistics for number of occasions will be presented in the same time intervals. Multiple occurrences of rescue medication within 15 minutes will only count as one occurrence.

The type of rescue medication taken will also be summarized in the same time intervals per flare.

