## **18 Derived and computed variables**

### **18.1 Unpermitted rescue medication**

Unpermitted rescue medication that leads to exclusion from PP population is defined as more than one incorrect intake, i.e. either type or outside time window (multiple incorrect intakes within 15 minutes is counted as one):

- Unpermitted type
  - Types other than paracetamol/acetaminophen and/or codein or tramadol or rescue medications classified as non-medicinal products (e.g. ice/cold pack, vinegar) and taken between treatment start and 72 hours.
  - Glucocorticoids (from general concomitant medication and rescue medication) taken between treatment start and 72 hours).
  - All unresolved OTHER <72 hours.

- Outside time window
  - All rescue (from rescue medication) taken prior to the 24 hours VAS pain assessment. If 24 hours VAS pain is missing, taken within 24 hours since treatment start.
  - All rescue (from rescue medication) taken within 6 hours prior to the 48 hours VAS pain assessment. If 48 hours VAS pain is missing, taken within 42 to 48 hours since treatment start.
  - All rescue (from rescue medication) taken within 6 hours prior to the 72 hours VAS pain assessment. If 72 hours VAS pain is missing, taken within 66 to 72 hours since treatment start.
  - All rescue (from rescue medication) with a missing timestamp (date and time) that can be related to a flare.

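### The consistency forest plot splits patients by rescue use, which happens after randomization in response to pain, so those two rows can misstate a uniform treatment effect

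*SAP*

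**What the plan says.** SAP 14.1.1 gives its purpose as "In order to examine the consistency of the treatment effect". It fits the primary MMRM within each subgroup of the ITT population, reports the anakinra-minus-triamcinolone difference with a 95% confidence interval and no p-value, repeats this for each dose, and plots the pooled differences in a forest plot. Six of the seven factors are fixed at baseline: ULT use, BMI, age, sex, race and renal function. The seventh is "Usage of rescue medication up to 72 hours during for the first flare (yes/no". No caveat sets it apart.

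Protocol 9.3.9, headed as exploratory, has the same factor without the time limit: "usage of rescue medication during the first flare (yes/no". SAP Section 5, which lists changes from the protocol, does not record the narrowing to 72 hours.

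Protocol 7.5.5.4 says patients who have difficulty tolerating their pain are "allowed to take rescue medication as needed after the 24-hour post-dose pain assessment". The primary endpoint averages the 24-, 48- and 72-hour scores. SAP 3.3.2 lists "Time to intake of rescue medication from first IMP administration" among the secondary efficacy endpoints, and SAP 14.3.1.5 compares it between arms: "Time to first intake of rescue medication during the first flare will be analyzed using a stratified log-rank test".

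**The concern.** A consistency plot is readable because each row is a randomized comparison within a group defined before treatment. Rescue use breaks that condition. The plan itself regards rescue as something treatment may change, since it tests rescue between arms, and it is prompted by the pain that the primary endpoint measures.

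Suppose anakinra lowers pain. Some patients who would have taken rescue on triamcinolone then do not take it on anakinra. Those still taking rescue on anakinra are a more selected, harder-to-treat group than those taking it on triamcinolone. The anakinra patients without rescue include people who would have needed it on triamcinolone. Both rows then compare unlike patients, and a reader could see heterogeneity or attenuation that does not exist.

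SAP Section 2 says the planned analyses will feed regulatory submissions or manuscripts. Protocol 5.2 gives dose selection as an aim, and 14.1.1 repeats the split by dose.

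**Working it through.** **Planning figures, reproduced.** SAP Section 7 gives a difference of 12 mm, SD 25 mm, two-sided 5%, 80% power and 106:53 allocation.

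- Control-arm size = 1.5 × (1.960 + 0.842)² × 25² / 12² = 51.1, so 52, and 156 in total, against 159 planned.
- Power at 106:53 (normal approximation): 12 / (25 × √(1/106 + 1/53)) = 2.85; Φ(2.85 − 1.96) = 81.4%.

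The stated figures hold, and the rescue split has no bearing on them.

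**Why the rows differ from the overall effect.** Let r_A and r_T be the rescue proportions on anakinra and triamcinolone, D_yes and D_no the two row differences (anakinra minus triamcinolone), and G the gap in mean change between rescued and non-rescued triamcinolone patients. Then, exactly,

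overall = r_A·D_yes + (1 − r_A)·D_no − (r_T − r_A)·G.

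The last term is the part of the effect that works by keeping patients out of the rescue group. It appears in neither row. It is zero if the rescue rates are equal or if rescued and non-rescued patients do not differ.

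**Simulation set 1.** 600,000 patients per scenario, 2:1 allocation, SD of the averaged change 25 mm, uniform 12 mm effect at 24, 48 and 72 hours, and no effect of rescue on pain. Assumptions not in the documents:

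- baseline about 75 mm (SD 12, limited to 50–100);
- triamcinolone mean change −25, −35 and −45 mm at the three times;
- within-patient correlation 0.5 or 0.7;
- rescue probability logistic in the 24-hour score, with scale 5 or 15 mm;
- triamcinolone rescue rate 30%, 50% or 70%.

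| Triamcinolone rescue | Anakinra rescue | Rescue-yes row (mm) | Rescue-no row (mm) | All patients (mm) |
|---|---|---|---|---|
| 30% | 18–21% | 6.4–8.8 | 8.6–9.9 | 11.9–12.1 |
| 50% | 35–39% | 7.0–9.3 | 7.4–9.4 | 12.0–12.1 |
| 70% | 56–59% | 7.8–9.7 | 6.7–8.9 | 11.9–12.1 |

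Entries are the advantage of anakinra. Checking the identity at 50% rescue, correlation 0.7 and scale 5 mm, where G was 31.6 mm: 0.35 × (−7.0) + 0.65 × (−7.4) − 0.15 × 31.6 = −2.45 − 4.81 − 4.74 = −12.0 mm.

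**Simulation set 2.** This set has lower overall rescue (25% or 45%) and a wider range of pain dependence: baseline 72 mm (SD 13), triamcinolone means 58, 50 and 42 mm, correlation 0.3, 0.5 or 0.7, and logistic scale 5 to 60 mm. The resulting SD of the change is 19–23 mm. It has 30 scenarios, and both rows were below 12 mm in all of them.

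| Dependence of rescue on 24-hour pain | Rows (mm) |
|---|---|
| Weak (scale 40–60 mm) | 11.4–11.9 |
| Moderate (20 mm) | 10.0–11.0 |
| Steep (5–10 mm) | 6.3–10.2 |

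**Controls.** With no treatment effect, the rows are about 0 in both sets. With rescue unrelated to pain, they are 11.9 to 12.1 mm.

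**If rescue works.** When rescue lowers the 48- and 72-hour scores by 10 mm (set 1, correlation 0.7, scale 5 mm), the rows are 6.1 and 8.5 mm at 30% triamcinolone rescue and 7.0 and 7.5 mm at 50%. The overall figures are 11.2 and 11.0 mm.

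**Precision.** At SD 25 and rescue proportion r in both arms, the rescue-yes half-width is 1.96 × 25 × √(1/(53r) + 1/(106r)). This gives 15.1 mm at r = 0.3 (9.9 mm for the no row) and 11.7 mm for both rows at r = 0.5. For the whole trial it is 8.2 mm.

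**The case against.** Nobody need defend the split as causal to call this minor. The protocol labels the whole set exploratory, the trial is a phase 2 exploratory study, p-values are withheld, and no decision hangs on these rows. All of that stands.

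The size rests wholly on assumptions. In 18 of the 30 scenarios of set 2 the shortfall is at most 2.0 mm, and in every scenario it is smaller than the row's own confidence half-width. That also stands, so the figures show a mechanism and not an expected bias. But a wide interval does not make a biased contrast informative about consistency.

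Set 2 uses an SD below the planned 25 mm, so its half-widths (7.1 to 14.8 mm) are somewhat too narrow. The set 1 figures, at SD 25, are the better guide to precision, and the attenuation persists there and when rescue is allowed to relieve pain.

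The subgroup and the secondary endpoint are not identical. One is a yes/no to 72 hours. The other is time to first intake, and SAP 18.22 leaves out ice packs and non-medicinal products. 14.1.1 does not say whether the same exclusions apply. The two share the same triggering event, which is what matters here.

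Other parts of the plan do deal with rescue. Patients are followed "irrespective of treatment withdrawal or use of rescue medication", so the ITT analysis answers a treatment-policy question, and the per-protocol set removes patients with more than one incorrect intake. Neither makes a comparison within rescue strata valid.

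**Conclusion.** The concern holds. Rescue use up to 72 hours is a consequence of pain after randomization, and its rows cannot support or refute consistency of effect. If treatment affects pain and rescue follows pain, both rows are distorted even when the effect is uniform. In every such scenario examined they were too small: by 0.1 to 5.7 mm across set 2, and by about 2 to 6 mm of 12 in set 1. Those sizes depend on assumed rescue rates, correlations and pain dependence, and the direction is established only for the models examined. There is no distortion if treatment does nothing or if rescue is unrelated to pain.

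The effect is limited to the two rows and the matching dose-level estimates. The primary ITT analysis, its type I error and power, and the other six subgroup factors are unaffected. The change should be made, but the trial's main conclusion does not depend on it.

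**What to change.** Delete the rescue line from the list in SAP 14.1.1 and from the forest plot, and add a sentence to SAP Section 5 recording the departure from Protocol 9.3.9. If the team wants to keep the split because the protocol names it, put it in a separate descriptive table labelled as post-randomization and not interpretable as a treatment effect, and still record in Section 5 the narrowing to 72 hours. Rescue use by arm stays fully reported under 14.3.1.5. The cost is one deleted line, one added sentence and the loss of one exploratory comparison.

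Optional, and not needed for the fix: if the influence of permitted rescue on the primary result is of interest, add one supplementary analysis in the full ITT population. Set the 48- and 72-hour scores after first rescue intake to missing, multiply impute them under a stated missing-at-random assumption, and use the primary contrast. This answers a different question from the treatment-policy analysis. It also costs more: rescue times must be combined from the eDiary and the two eCRF forms, and a rule for incomplete times must be fixed in advance. SAP 18.1 counts as outside the permitted window "All rescue (from rescue medication) with a missing timestamp (date and time) that can be related to a flare", whereas 18.22 drops records with no date. Those rules serve different purposes and need not conflict, but a new analysis would have to state its own.

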#### **14.1.2 Sensitivity analysis of the primary endpoint**

To assess the robustness of the primary analysis results and conclusions on the treatment effect under varying assumptions, sensitivity analyses presented in Sections 14.1.2.1, 14.1.2.2 and 14.1.2.3 will be performed.

### 14.1.2.1 Sensitivity to subject population

The primary efficacy endpoint will be analyzed using an analysis identical to the primary analysis described in Section 14.1, but for the PP population.

### 14.1.2.2 Sensitivity to missing data handling

The primary efficacy analysis MMRM approach assumes that the underlying missing data mechanism is MAR. When the assumption of missing data being MAR is valid, the treatment effect estimated from the MMRM analysis is unbiased. However, this assumption may not hold in all circumstances and the possibility that the missingness mechanism is missing not at random (MNAR) should be explored (EMA 2010, National Research Council 2010, Little et al 2002, O’Kelly et al 2014). A sensitivity analysis will be performed to assess the robustness of results from the primary analysis to potential deviations from the MAR assumptions.

In this sensitivity analysis a distinction is made between intermittent missing values and monotone missing values. Intermittent missing values for a variable Y means that some values may be missing, say  $Y_j$  is missing, while there are values observed for the same patient at a later time point, i.e.  $Y_k$  is observed for some time point  $k > j$ . Patients with intermittent missing values are said to have a non-monotone missing data pattern. Monotone missing values are missing values where  $Y_j$  being missing implies that all  $Y_k$ ,  $k > j$ , are missing for that patient. A patient with only monotone missing values (and no intermittent missing values) is said to have a monotone missing data pattern.

In the sensitivity analysis, intermittent missing data are assumed to be MAR, while monotone missing values are assumed to be MNAR in the anakinra treatment groups. The analysis assumes that the missing outcomes on the different treatment arms vary independently, and includes scenarios where monotone missing values in the anakinra treatment arms have worse outcomes than monotone missing values in the triamcinolone treatment arm. Missing data in the triamcinolone group will be assumed to be MAR (intermittent as well as monotone missing values).

The tipping point analysis involves multiple imputation methodology, where each of the imputed datasets is analysed based on the same statistical model used for the primary analysis, i.e. a MMRM analysis of pain intensity VAS at time points baseline, 6, 12, 18, 24, 48 and 72 hours based on the ITT population.

#### 14.1.2.2.1 Exploration of missing data patterns

SAS PROC MI sorts the data into patterns based on whether the variables are missing or observed at each time point, and provides a default output dataset of missing data patterns. Mean pain intensity at each time point will be presented for each missing data pattern by treatment group.

### 14.1.2.3 Tipping point analysis

The sensitivity analysis will be based on a tipping point approach to assess how severe the departures from the MAR assumption must be in order to overturn a statistical significant result

to a non significant result for the primary analysis. This is done by evaluating several assumptions for the missing data mechanism until the tipping point is reached, i.e. where the study's conclusion changes. The deviation from the MAR assumption is reflected in the shift parameter. If the shift parameter at the tipping point is plausible the conclusions of the primary analysis under the MAR assumption is questionable.

For monotone missing data, the initial shift value will be zero, which represents MAR. The shift will remain at zero for the triamcinolone treatment group. For the anakinra treatment groups, the shift will be increased, and the process repeated until the study's conclusion changes, i.e. treatment effect is no longer significant.

The following steps show the process for the tipping point analysis:

1. Missing VAS values will be imputed based on the Markov-Chain Monte Carlo (MCMC) method (assuming MAR).

In this step, 500 complete datasets will be generated.

2. For subjects with monotone missing data in the anakinra treatment arms, monotone missing values will be imputed based on a MNAR model by adding a delta value to the MAR imputed value. Delta adjustment will be based on a scaled delta-adjustment approach in which the delta value added at each time point is defined as a percentage of the mean pain VAS at that time point. For the the triamcinolone group monotone missing values, imputed based on the MAR assumption in the first step, will not be adjusted.

In this step, the 500 datasets with complete data generated in step 1 will be updated.

3. The MMRM model used in the primary analysis will be fitted to the 500 imputed datasets generated in step 2. As in the primary efficacy analysis, the VAS scores from time points baseline, 6, 12, 18, 24, 48 and 72 hours will be included as response. Specification of the model and the contrast of primary interest will match the primary efficacy analysis. From each analysis of an imputation dataset, adjusted estimates of means, mean treatment differences and p-values will be obtained.
4. The results from the MMRM analyses of the 500 imputed datasets will be combined to obtain an overall estimate of the contrast of primary interest, i.e. the mean difference between the anakinra groups and the triamcinolone group in change from baseline to 24-72 hours in pain VAS score, as well as the p-value obtained after accounting for the uncertainty introduced by the missing data.
5. Steps 2 to 4 will be repeated by gradually increasing the values for the scaled delta adjustment until the scaled delta value is found that gives a p-value exceeding 0.05 (2-sided) or greater.

In the first step of the delta-adjustment, missing values are imputed based on a MCMC method assuming MAR. The MCMC sampling will be performed as implemented in PROC MI in SAS. The MCMC method will include a single chain with a burn-in of 1000, a thinning of 100 and non-informative priors for all parameters.

Treatment group and strata (ULT usage and BMI) are included in the variable list in the MCMC step. In this implementation, numeric dummy variables are created and included in the variable list together with the VAS pain intensity variables for time points 0, 6, 12, 18, 24, 48 and 72 hours. Because these dummy variables are observed for all patients, they are not imputed in the MCMC step, but contribute to the imputation model to allow for the mean pain intensity at different time points to depend on treatment and strata, while assuming the covariance structure across treatment and strata. This corresponds to the assumptions made in the analysis model used for the primary analysis.

In the second step, monotone missing values in the anakinra treatment arms are delta-adjusted where a delta value is added to the MAR imputed value. This approach corresponds to the third approach for pattern imputation with delta adjustment described [in Ratitch et al. \(2013\)](#).

The delta is defined in terms of percentage of the mean value at a given time point. Because the mean VAS pain intensity changes with time, the delta added to the MAR-imputed missing values will be different for different time points. Imputed values will be truncated at 100, since this is the maximum value possible for a VAS pain intensity measure. No rounding of values is performed in the imputation step.

In the third step, the complete datasets are analysed based on the same analysis model used for the primary analysis. In the fourth step, results across the different imputed datasets are combined based on the methodology of [Rubin \(1976\)](#) as implemented in PROC MIANALYZE.

Five hundred (500) imputations will be performed by using a random seed generated from the system clock in SAS. In the search for the tipping point, increasing values for the scaled delta will be investigated in steps of 5% of the time-specific mean pain intensity VAS.

In the fifth step, when potentially a tipping point has been found, LS Mean estimates and treatment differences with 95 % confidence intervals and p-value will be presented in a table for the choice of delta-adjustment that tip over the conclusions.

Since the tipping point analysis aims to find out how much of a change is required to “tip” the result from statistically significant to not statistically significant, it will not be performed for any comparison that is not statistically significant at the onset.

